7.5 Study Drug Exposure and Compliance

All patients should be informed that compliance with taking all oral medication as instructed is imperative. A site designee will phone the patient or the pharmacy on Day 1 to ensure that the prescription of ciprofloxacin was picked up and the first dose was taken. This phone call should be documented in the patient's source.

Patients will receive a dosing diary on Day 1 and be asked to record the dosing administration for the duration of the treatment period. The total amount of oral dosing completed during the treatment period will be documented in the eCRF.

A dosing summary will be presented for the ITT, m-MITT, CE and ME populations. The distribution of patients by the number of active doses of study drug therapy will be presented.

7.6 Efficacy Analyses

There is only one treatment group, so hypothesis testing is not needed. Only descriptive statistics will be presented for each endpoint, which will mainly consist of frequency and percentage for each category of the endpoint.

The reasons for non-responder and indeterminate will be summarized for most endpoints.

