9.5 Efficacy Analysis

9.5.1 Analysis of Primary Outcome Measure

The primary outcome is overall response (clinical plus microbiologic) at the Day 12 (+/- 1 day) visit in the m-MITT population. The number and percentage of responders, non-responders and indeterminates will be determined.

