5.2 Secondary Efficacy Outcome Measure

All symptomatic subjects enrolled in the study will have a positive urine dipstick for both leukocyte esterase and nitrite. The number and percentage of subjects who go on to have a positive baseline urine culture for $\geq 10^5$ CFU/mL of a uropathogen will be evaluated.

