6 STATISTICAL METHODS

6.1 Sample Size

The study is designed to determine the clinical and microbiologic efficacy of ciprofloxacin for adult female patients with uUTI, due to either a ciprofloxacin susceptible or non-susceptible organism. Two-hundred fifty (250) symptomatic patients will be enrolled with the expectation that there will be no screen failures. Of the 250 enrolled patients, we expect 50 will not have a positive urine culture for $\geq 10^5$ CFU/mL of a uropathogen at baseline. Of the 250 enrolled patients, we expect 40 will have a uUTI due to a ciprofloxacin non-susceptible organism.

Patients who withdraw prior to initial dose, will be replaced to ensure a total of 250 patients

will receive at least a single-dose of ciprofloxacin.

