6.6 Comments on Statistical Analysis

The following general comments apply to all statistical analyses and data presentations:

- Summaries will include frequency and percentages for categorical data; frequency and median for ordinal data; and number, mean, standard deviation, and median, minimum and maximum for continuous data.
- Duration variables will be calculated using the general formula: (end date start date) +1 for end dates after first dose and (end date start date) for end dates before first dose.
- If the reported value of a clinical laboratory parameter cannot be used in a statistical summary table (e.g., a character string is reported for a parameter of the numerical type),

a coded value must be appropriately determined and used in the statistical analyses. In general, a value or lower and upper limit of normal range such as '<10' or ' \leq 5' will be treated as '10' or '5' respectively, and a value such as '>100' will be treated as '100'. However, the actual values as reported in the database will be presented in data listings.

- Individual patient listings of all data represented on the eCRFs will be provided to facilitate the investigation of tabulated values and to allow for the clinical review of all efficacy and safety parameters.
- Version 9.4 of SAS® statistical software package will be used to provide all summaries, listings, graphs, and statistical analyses.

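### SAP 7.6 pre-specifies no confidence interval for the primary response rate, the dipstick percentage or the susceptible versus non-susceptible comparison, although the study aims to estimate them

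*SAP*

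**What the plan says.** SAP 7.6 gives its reason first, "There is only one treatment group, so hypothesis testing is not needed", and then the consequence: "Only descriptive statistics will be presented for each endpoint, which will mainly consist of frequency and percentage for each category of the endpoint". The general rule in SAP 6.6 agrees with this: "Summaries will include frequency and percentages for categorical data; frequency and median for ordinal data". Neither passage mentions an interval.

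The sections on individual endpoints follow the same pattern. SAP 5.1 defines the primary proportion by a formula only. Protocol 9.5.1 says of the primary outcome: "The number and percentage of responders, non-responders and indeterminates will be determined". SAP 5.2 describes the dipstick outcome as "The number and percentage of subjects who go on to have a positive baseline urine culture" at the 10^5 CFU/mL threshold. Protocol 9.3 promises to compare response rates between susceptible and non-susceptible infections, and protocol 9.5.1.1 repeats the split, but neither document gives a method for the comparison. The SAP's list of differences from the protocol (Section 8) does not say the comparison was dropped.

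Confidence interval appears only in the protocol's abbreviation list, and SE only in the SAP's. No analysis section uses either.

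On purpose, SAP 6.1 says: "The study is designed to determine the clinical and microbiologic efficacy of ciprofloxacin for adult female patients with uUTI", for susceptible and non-susceptible organisms alike. It gives expected counts, including "we expect 40 will have a uUTI due to a ciprofloxacin non-susceptible organism", but no power, target rate or precision.

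**The concern.** The first step in SAP 7.6 is sound: with one arm there is no treatment contrast to test. The second step, from no test to counts and percentages alone, does not follow. A response rate estimated in a sample has sampling error whether or not a hypothesis is tested, and an interval is the ordinary way to report it.

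The sample-size section gives no precision either, so the documents nowhere say how accurately 250 patients answer the question. This matters most for the non-susceptible subset. The protocol's rationale (1.2.1) describes response to fluoroquinolones in resistant infection as poorly studied, and only about 40 such patients are expected. Two percentages side by side, one from about 160 women and one from about 40, give no indication of how much of the gap between them could be chance.

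**Working it through.** **Plan's own figures.** The 250 cannot be reproduced, because the documents state no alpha, power, target rate or precision goal. Only the implied counts can be derived from SAP 6.1:

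- Culture-positive: 250 − 50 = 200, so the expected dipstick percentage is 200/250 = 80%.
- Susceptible: 200 − 40 = 160, if all 40 non-susceptible patients are among the 200.

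The 200 is an upper bound for the m-MITT at these planned counts. SAP 4.4 also excludes entry cultures with more than two species, and SAP Appendix 3 limits the m-MITT to Enterobacteriaceae and/or *S. saprophyticus*. The 40 are counted among the enrolled, not within the m-MITT, so the 160/40 split is an assumption.

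**Assumptions.** The 95% two-sided level and the response rates are mine. The documents give no expected response rate, so a range of 50% to 90% is shown.

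**Formula.** With z = 1.96, the Wilson interval has centre (p + z²/2n)/(1 + z²/n) and half-width z·√(p(1−p)/n + z²/4n²)/(1 + z²/n). Exact (Clopper-Pearson) limits are given alongside.

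- Dipstick, p = 0.80, n = 250: centre 0.8077/1.0154 = 0.7955; half-width 1.96 × √(0.00064 + 0.0000154)/1.0154 = 0.0494.
- Non-susceptible, p = 0.50, n = 40: centre 0.5480/1.0960 = 0.50; half-width 1.96 × √(0.00625 + 0.00060)/1.0960 = 0.148.

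| Quantity | Count | Wilson 95% | Exact 95% | Half-width, exact (points) |
|---|---|---|---|---|
| Dipstick percentage | 200/250 (80%) | 74.6 to 84.5 | 74.5 to 84.8 | 5.1 |
| Overall response, n = 200 | 100 (50%) | 43.1 to 56.9 | 42.9 to 57.1 | 7.1 |
| | 140 (70%) | 63.3 to 75.9 | 63.1 to 76.3 | 6.6 |
| | 180 (90%) | 85.1 to 93.4 | 85.0 to 93.8 | 4.4 |
| Non-susceptible, n = 40 | 20 (50%) | 35.2 to 64.8 | 33.8 to 66.2 | 16.2 |
| | 28 (70%) | 54.6 to 81.9 | 53.5 to 83.4 | 15.0 |
| | 36 (90%) | 76.9 to 96.0 | 76.3 to 97.2 | 10.4 |

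**Difference, susceptible minus non-susceptible (Newcombe).** For d = p₁ − p₂ with Wilson limits (l, u), the lower limit is d − √((p₁−l₁)² + (u₂−p₂)²) and the upper limit is d + √((u₁−p₁)² + (p₂−l₂)²).

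- 128/160 (80%, Wilson 73.1 to 85.5) versus 28/40 (70%, Wilson 54.6 to 81.9): lower 0.10 − √(0.0687² + 0.1193²) = −0.038; upper 0.10 + √(0.0546² + 0.1543²) = 0.264. The observed 10 points are compatible with anything from −3.8 to 26.4.
- 128/160 versus 20/40: d = 30 points, interval 13.7 to 45.8.

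The same observed gap could therefore be chance or substantial, depending on figures the plan does not commit to report.

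**The case against.** A reader might infer that the trial cannot say how precise its rates are. The documents do not support that. The primary and dipstick results are to be reported as counts with percentages, and for a single binomial proportion the count and denominator determine the interval once a method and level are chosen. Anyone with the two subset counts can also compute an interval for their difference.

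A reader might also infer that SAP 7.6 forbids intervals. It says the output will mainly, not solely, be frequencies and percentages, and the protocol allows exploratory analyses. The text is silent on intervals; it does not exclude them.

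The design sections (protocol Section 3, SAP Section 2) speak of documenting response, and there is no success criterion for an interval to inform. On that view the omission is weak reporting in a declared descriptive study and contradicts nothing in the plan. Nor does either document mention a later trial to be planned from these rates, so no harm can be claimed there.

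All of this stands and limits the point. What remains is that the choice of method and level is left until after the data are seen. At 20/40 the exact interval is 33.8 to 66.2 and the Wilson 35.2 to 64.8. A SAP that calls itself a priori should settle that choice, and the comparison promised in protocol 9.3 still has no method.

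**Conclusion.** The concern holds as a matter of pre-specified reporting. No estimate, denominator or patient classification is wrong, and nothing is lost irrecoverably. The plan does leave its primary rate, its secondary percentage and its one promised comparison without any stated measure of precision.

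The effect is modest for the primary rate (about 4 to 7 points either side) and the dipstick percentage (about 5). It is large for the non-susceptible subset (about 10 to 16), where it could change how the result is read. These sizes rest on a 95% level, on assumed response rates of 50% to 90%, and on the expected counts in SAP 6.1. If the m-MITT falls below 200, or fewer than 40 non-susceptible patients enter it, the intervals widen at a given rate.

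This is a cheap improvement that the sponsor should make; it is not a flaw that invalidates the analysis.

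**What to change.** In SAP 7.6, state that two-sided 95% confidence intervals, by Wilson or exact method with one named in advance, will accompany:

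- Day 12 overall response in the m-MITT;
- the same rate in the ciprofloxacin-susceptible and non-susceptible subsets;
- the dipstick percentage in SAP 5.2.

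Add a 95% Newcombe interval for the susceptible minus non-susceptible difference. Label all of these descriptive and unadjusted for multiplicity, since a difference interval will otherwise be read as a test. There is no need to extend intervals to every pathogen or ESBL stratum, where cells may be very small.

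In SAP 6.1, state the expected half-widths over assumed response rates of 50% to 90%: about 4 to 7 points at n = 200 (noted as an upper bound for the m-MITT), about 10 to 16 points at n = 40, and about 5 points for the dipstick percentage at 200/250.

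The cost is two short SAP edits and slightly more table output, with no new data or patients. The downside for the sponsor is that the intervals will show plainly how imprecise the non-susceptible estimate is.

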7.7 Interim Analysis

N/A

7.8 Safety Analyses

Safety analysis will be conducted in the safety population. Safety parameters include adverse events.

Verbatim descriptions of AEs will be coded using Version 21.0 or higher of MedDRA. Summary tables will be provided for all treatment-emergent AEs (TEAEs). An AE is defined as any untoward medical occurrence in a clinical investigation patient administered a product or medical device, unless the event is captured in the study endpoint, as defined below; the event need not necessarily have a causal relationship with the treatment or usage. ATEAE is any AE that newly appeared, increased in frequency, or worsened in severity following initiation of ciprofloxacin. In addition, all AEs (including non-TEAEs), serious TEAEs, and TEAEs leading to study drug discontinuation will be provided in listings containing patient number, verbatim term, MedDRA system organ class and preferred terms, seriousness flag, intensity, relationship to study drug, action taken and outcome.

An overall summary of AEs will include number of patients who experienced at least one AE of the following categories: any AE, any TEAE, any drug-related TEAE defined as possibly or probably related to study drug, any serious TEAE, any drug- related SAE, any SAE leading to death, any TEAE leading to premature discontinuation of study drug, and any SAE leading to premature study drug discontinuation.

The number and percentage of patients reporting a TEAE will be tabulated by system organ class and preferred term for all TEAEs and TEAEs through TOC. TEAEs through TOC will also be summarized separately by system organ class, preferred term, and intensity (mild, moderate, and severe); and by system organ class, preferred term, and relationship (unrelated or related to study drug). A table will provide all SAEs (through TOC) by system organ class and preferred term. For all analyses of TEAEs, if the same AE (based on preferred term) is reported for the same patient more than once, the AE is counted only once for that preferred term and at the highest intensity and strongest relationship to study drug.

Analysis of the distribution of the duration of each adverse event as well as an overall mean adverse event duration will be presented.

If an AE starts on the same day that dosing is initiated, and the start time of the AE is missing then the AE is considered TEAE.

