8.2 Reporting Period

Adverse events will be collected from the time that the patient provides informed consent through TOC.

For SAEs, the reporting period to Iterum Therapeutics begins from the time that the patient signed informed consent, which may be prior to the patient's participation in the study, i.e., prior to undergoing any study-related procedure through the TOC. Any SAE occurring any time after the reporting period must be promptly reported if a causal relationship to investigational product is suspected

All AEs should be recorded on the CRF if they occur from the time the patient provides informed consent through TOC.

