8.12.2 Non-SAE Reporting Requirements

All AEs will be reported on the AE page(s) of the CRF. Please note that while all AEs are reported on the AE page of the CRF, there is an additional form used for collection of SAE information, as described in Section 8.12.1, which is not the same as the AE CRF. When the same data are collected, the two forms must be completed in a consistent manner. For example, the same AE term should be used on both forms. Serious adverse events should be reported using concise medical terminology on the CRFs as well as on the form for collection of SAE information. The information on the AE CRF and the SAE form must be the same and will be reconciled at defined periods throughout the study to ensure that they do.

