9.6 Safety Analyses

Safety will be assessed through summaries of AEs. All safety analyses will be based on the Safety population.

Summary tables of treatment-emergent AEs (TEAEs) will be provided. A TEAE is any AE that newly appeared, increased in frequency, or worsened in severity following initiation of ciprofloxacin. The incidence of TEAEs will be tabulated by system organ

class and preferred term, and by severity and relationship to treatment. Tables of TEAEs leading to ciprofloxacin discontinuation, withdrawal from the study or an SAE will be provided. AEs occurring prior to the first dose of ciprofloxacin (AEs are recorded from the time of informed consent) will be provided in a listing.

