Appendix 4 Ciprofloxacin Tablets – USPI

HIGHLIGHTS OF PRESCRIBING INFORMATION

These highlights do not include all the information needed to use CIPRO safely and effectively. See full prescribing information for CIPRO.

CIPRO® (ciprofloxacin hydrochloride) tablet, for oral use

CIPRO® (ciprofloxacin hydrochloride), for oral suspension

Initial U.S. Approval: 1987

WARNING: SERIOUS ADVERSE REACTIONS INCLUDING TENDINITIS, TENDON RUPTURE, PERIPHERAL NEUROPATHY, CENTRAL NERVOUS SYSTEM EFFECTS AND EXACERBATION OF MYASTHENIA GRAVIS

See full prescribing information for complete boxed warning.

- Fluoroquinolones, including CIPRO*, have been associated with disabling and potentially irreversible serious adverse reactions that have occurred together (5.1), including:
- Tendinitis and tendon rupture (5.2) Peripheral neuropathy (5.3)
- o Central nervous system effects (5.4)

Discontinue CIPRO immediately and avoid the use of fluoroquinolones, including CIPRO, in patients who experience any of these serious adverse reactions (5.1)

- Fluoroquinolones, including CIPRO, may exacerbate muscle weakness in patients with myasthenia gravis. Avoid CIPRO in patients with known history of myasthenia gravis. (5.5)
- Because fluoroquinolones, including CIPRO, have been associated with serious adverse reactions (5.1-5.15), reserve CIPRO for use in patients who have no alternative treatment options for the following indications:

 Acute exacerbation of chronic bronchitis
 O Acute uncomplicated cystitis (1.11)
 Acute sinusitis (1.12)

----- RECENT MAJOR CHANGES -----

--- INDICATIONS AND USAGE -----

Boxed Warning	M/2016 Indications and Usage (1.10, 1.11, 1.	2) M/2016 Dosage and Administration, Dosage in Adults (2.1) M/201
Warnings and Pred	eautions (5.1)	M/2016

CIPRO is a fluoroquinolone antibacterial indicated in adults (≥18 years of age) with the following infections caused by designated, susceptible bacteria and in pediatric patients where indicated: • Skin and Skin Structure Infections (1.1)

- Bone and Joint Infections (1.2)
- Complicated Intra-Abdominal Infections (1.3)
- Infectious Diarrhea (1.4)
- Typhoid Fever (Enteric Fever) (1.5)
- Uncomplicated Cervical and Urethral Gonorrhea (1.6)
- Inhalational Anthrax post-exposure in adult and pediatric patients (1.7)
- Plague in adult and pediatric patients (1.8)
- Chronic Bacterial Prostatitis (1.9)
- Lower Respiratory Tract Infections (1.10)

 Acute Exacerbation of Chronic Bronchitis

every 12 hours

single dose

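### SAP 7.8 stops the SAE, intensity and relationship tables at TOC, although suspected drug-related SAEs stay reportable afterwards and their route into the safety outputs is not stated

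*SAP*

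**What the plan says.** **Reporting.** Protocol 8.2 sets the routine period: "Adverse events will be collected from the time that the patient provides informed consent through TOC". SAEs follow the same period, with one extension that has no end date: "Any SAE occurring any time after the reporting period must be promptly reported if a causal relationship to investigational product is suspected".

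**Recording.** Protocol 8.2 ties the CRF to the routine period: "All AEs should be recorded on the CRF if they occur from the time the patient provides informed consent through TOC". Protocol 8.12.2 gives no window: "All AEs will be reported on the AE page(s) of the CRF". The same section requires the AE page and the SAE form to agree and to be reconciled during the study.

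**Planned tables in the protocol.** Protocol 9.6 plans TEAE incidence by severity and by relationship to treatment, and adds: "Tables of TEAEs leading to ciprofloxacin discontinuation, withdrawal from the study or an SAE will be provided". It attaches no TOC limit to any of these.

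**Planned tables in the SAP.** SAP 7.8 limits the SAE table: "A table will provide all SAEs (through TOC) by system organ class and preferred term". It does the same for intensity: "TEAEs through TOC will also be summarized separately by system organ class, preferred term, and intensity (mild, moderate, and severe"). The same sentence covers the table by relationship. SAP 7.8 also plans a table of TEAEs by system organ class (SOC) and preferred term (PT) in two versions, one for all TEAEs and one through TOC. It sets no TOC limit on the overall AE summary or on the listings. SAP 8, which lists departures from the protocol, does not mention the limit.

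**The concern.** After TOC, the only events the protocol still requires to be reported are serious and suspected to be caused by the drug. A TOC limit on the SAE table and on the relationship table therefore removes exactly that class of event from the two outputs where a reader would look for it first. The label appended to the protocol says that fluoroquinolones "have been associated with disabling and potentially irreversible serious adverse reactions that have occurred together", so a late serious reaction is not a remote idea for this drug.

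The SAP allows for TEAEs after TOC, since it plans the SOC/PT table both with and without the limit. Yet the tables that break events down by seriousness, intensity or relationship exist only in the limited version, and no reason is given.

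A second question lies behind the first. If a late SAE is recorded only on the SAE form, outputs built from the eCRF would not contain it, whether or not they carry a TOC limit.

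**Working it through.** The plan gives no figure to reproduce on this point. The check is a reading of the sections side by side.

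**Step 1: the interval.** TOC is Day 12 ± 1, that is Day 11 to 13 (Protocol 6.3.1). The only later scheduled contact is the call at Day 21 ± 3, that is Day 18 to 24 (Protocol 6.3.2), and its stated purpose is symptom resolution. The gap runs from 18 − 13 = 5 days to 24 − 11 = 13 days. The duty in Protocol 8.2 covers this gap and any time after it.

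**Step 2: would a late SAE be a TEAE?** Yes. Protocol 9.6 and SAP 7.8 define a TEAE by its onset or worsening after the start of ciprofloxacin and set no end date.

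**Step 3: where would it appear, if it is in the analysis database?**

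| SAP 7.8 output | TOC limit | Late suspected-related SAE shown? |
|---|---|---|
| Overall AE summary (includes rows for serious TEAEs and drug-related SAEs) | none stated | yes |
| TEAEs by SOC/PT, all | none | yes |
| TEAEs by SOC/PT, through TOC | yes | no |
| TEAEs by SOC/PT and intensity | yes | no |
| TEAEs by SOC/PT and relationship | yes | no |
| SAEs by SOC/PT | yes | no |
| Listings (with seriousness, intensity and relationship) | none stated | yes |

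The through-TOC SOC/PT table has an uncut partner. The intensity, relationship and SAE tables do not.

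**Step 4: would it be in the database?** Under Protocol 8.2 alone, CRF entry ends at TOC and the event could exist only on the SAE form. Under Protocol 8.12.2, every AE goes on the CRF and must match the SAE form. SAP 7.8 names no data source for SAEs, while SAP 6.6 describes the patient listings as listings of eCRF data. If 8.2 governs and the outputs come from the eCRF, the uncut outputs in Step 3 could miss the event too. The documents do not settle which section governs.

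**Step 5: size.** The documents give no rate of late related SAEs. Purely as an illustration, let p be an assumed rate per patient, with 250 treated women and independent events. The chance that at least one occurs is 1 − (1 − p)^250:

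- p = 0.1%: 1 − 0.999^250 = 22%
- p = 0.4%: 1 − 0.996^250 = 63%
- p = 1%: 1 − 0.99^250 = 92%

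The range shows how strongly the answer depends on p; none of the three rates has support in the documents. For one such event, the SAE table would read 0/250 instead of 1/250 (0.4%).

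**The case against.** The strongest defence is that the limit matches the period of complete ascertainment. AEs are sought from consent through TOC, the schedule of activities has no AE collection after that, and Protocol 13.1 defines the end of study as the TOC visit. Later reports are passive and confined to suspected-related SAEs. Adding them to a table with 250 as denominator mixes two kinds of ascertainment. This stands as a reason to keep a through-TOC version and to flag later events. It does not justify leaving a known, suspected drug-related SAE out of the only SAE table.

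It can also be said that Protocol 9.6, read together with 8.2, already covers only the period through TOC, so the SAP merely restates it. That reading is possible. The protocol is silent here rather than contradicted, and for this reason the point rests on an unstated restriction, not on a proven conflict.

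Two stronger readings are tempting. A reader might infer that late SAEs disappear from the report. The documents do not support that: an event in the database is shown in the overall summary, the all-TEAE table and the listings, and under Protocol 8.12 such events also go to the sponsor, and onward to the FDA and the manufacturer. A reader might also infer that the report would give contradictory SAE counts. The counts could differ, but the SAE table is labelled as running through TOC, so the difference would be a labelled one.

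Finally, if the event sits only on the SAE form, deleting the TOC limit changes nothing by itself. That is correct, and it is why the fix must also name the data source.

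**Conclusion.** The point holds for three outputs: SAEs by SOC/PT, TEAEs by intensity and TEAEs by relationship. As written, they exclude the one class of event that Protocol 8.2 keeps reportable after TOC, and neither Protocol 9.6 nor SAP 8 states this restriction. For an event in the database, what is lost is its place in those three tables, not its presence in the report. Whether it reaches the database depends on how Protocol 8.2 and 8.12.2 are reconciled; the further loss from the uncut outputs arises only if 8.2 governs and the outputs are built from the eCRF.

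The number of events affected is unknown, and the percentages in the working must not be read as estimates for this trial. No primary or secondary objective is touched. Severity is minor to moderate.

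**What to change.** - **SAP 7.8, SAE table:** present all reported SAEs and flag those with onset after TOC.
- **SAP 7.8, intensity and relationship tables:** run each for all TEAEs and through TOC, as the SAP already does for the SOC/PT table.
- **Protocol 8.2 and 8.12.2:** reconcile the two statements on CRF recording.
- **SAP 7.8, data source:** state how post-TOC SAEs already reported to the sponsor enter the summary, the tables and the listings.
- **SAP 8:** if any table stays limited to TOC with no uncut version, declare it there.

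The cost is a few words in the SAP, a sentence in the protocol and, depending on how the recording rule is settled, a few extra CRF entries. No visit is added and the Day 21 call does not change. The small downside is that post-TOC events are passively ascertained, so a footnote must say that they are not comparable with events collected through TOC.
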